3.3. Study Exposure

The exposure of interest is COVID-19 vaccination in pregnancy. Participants will be those who receive a Health Canada approved COVID-19 vaccine (any product, any number of doses) during pregnancy.

Participants will be recruited *before* they are fully vaccinated and are pregnant with a viable fetus.

3.4. Study Outcomes

3.4.1. Primary Outcomes

[figure not shown]
The primary outcome of interest will be immunogenicity of COVID-19 vaccines. We will measure:

- Seroconversion rates in vaccinated mothers
- SARS-CoV-2 antibody titres and their persistence in mothers after vaccination in pregnancy
- Transfer of antibodies to breastmilk/chestmilk
- Transfer and persistence of SARS-CoV-2 antibodies to the neonate/infant over the study period.
- Other immune response markers in mothers and infants
- Comparing infection-acquired and vaccine-acquired immunity against COVID-19 in mothers and newborns (Objective 3: COPE Substudy)
- Comparing immune responses to COVID-19 vaccination in pregnant and non-pregnant women/individuals (Objective 4: SSO Substudy)

3.4.2. Secondary Outcomes

Secondary outcomes will be those related to vaccine safety for maternal, pregnancy and newborn health.

- Secondary perinatal outcomes will include: maternal (death, non-delivery hospitalization, any infection, preterm labour, hypertensive disorders of pregnancy, placental abruption, postpartum hemorrhage), and newborn (preterm birth [<37 weeks], small-for-gestational-age [<10 th percentile for gestational age and sex-specific birth weight],⁷ fetal loss/stillbirth, term low birthweight [<2500 g], 5-minute Apgar score ≤ 5 , cord blood pH <7.0 , length of hospital stay for the birth admission, admission to neonatal ICU for >12 hours; and a composite neonatal adverse outcome indicator [NAOI], which includes congenital anomalies).^{8,9}
- Secondary postpartum outcomes will include: infant growth, frequency of infection (e.g., influenza, pneumonia, sepsis, acute respiratory infections, gastrointestinal), rates of re-hospitalization and emergency department visits during the follow-up period, and a composite indicator for pediatric complex chronic conditions namely:¹⁰ neurologic and neuromuscular; cardiovascular; respiratory; renal and urologic; gastrointestinal; hematologic or immunologic; metabolic; other congenital or genetic defect; and malignancy. Finally, we will note infant deaths at any time during the study.

3.5. Study Procedures

3.5.1. Participant Recruitment

Self-Identification

Women/Individuals will have the opportunity to self-identify to participate in the study.

- Recruitment posters and brochures will be distributed throughout the clinical care areas of participating hospital sites.
- Recruitment posters and brochures will be posted at COVID-19 vaccine clinics.
- Recruitment posters and brochures will be distributed to the offices of obstetricians and family physicians, midwifery clinics and birth centres, private clinics and other establishments within the study catchment area in order to increase awareness and profile of the birth cohort.
- We will also advertise the study more widely, online and through the professional and personal social media accounts of participating investigators and institutions.

Active recruitment from antenatal clinics

Participants will also be actively recruited from participating perinatal care settings where possible.

3.5.2. Participant Screening

Self-Identification Participant Screening

Potential participants may self-refer via the PLAN-V website and be screened for eligibility by a member of the research team at the SCC. Screening logic is summarized in **Figure 1**. After eligibility is confirmed, the SCC will inform the Site Investigator/Delegate at the participating hospital site geographically closest to the participant. Site Investigator/Delegates will then take on the responsibility of contacting the participant for consent, enrollment and follow-up for data and sample collection.

[figure not shown]
[figure not shown]

Figure 1. Screening logic applied to women/individuals interested in participating in the study.

Antenatal Clinics Participant Screening

There is more than one option for participant screening within the perinatal care setting.

1. A member of the potential participant's circle of care (healthcare provider (HCP)) identifies an individual as eligible for participation in the study, based on the inclusion/exclusion criteria, and approaches the individual to see if they would be interested in learning more about the study from the study team. If

the individual is interested, the HCP informs the study team that the potential participant would like to learn more, the potentially eligible participant contacts the study team based on locally approved methods.

2. A study team member screens the local institutional electronic medical record (EMR) and/or medical charts for participant eligibility. Potential participants identified are contacted by study team as per local institutionally approved methods.

3.5.3. Participant Consent and Enrollment

Written informed consent (via wet ink signature, verbal consent with deferred wet ink signature, scanned/photo copy of wet ink signature or electronic signature where permitted by the participating hospital site research ethics board) will be obtained from the participant prior to performing any protocol-specific procedures.

Participants will provide consent for themselves and on behalf of their infants.

The Site Investigator/Delegate will discuss with each participant the nature of the study and the study requirements and restrictions. Consent form review will be conducted in-person, over the phone, or via video conference using a locally-approved, licensed institutional video conferencing platform. The participant will be informed of their right to withdraw from the study at any time for any reason without prejudice to future care, and with no obligation to give the reason for withdrawal. The participant will be allowed as much time as required to consider the information. They will have the opportunity to question the Site Investigator/Delegate and consult with their primary care provider or other independent parties (e.g., their partner).

We will employ a consent model, in which participants consent to the current study as well as secondary use of collected data and samples. Our consent will cover consent to obtain data from participant medical charts, enable linkage of participant records with birth registry and health administrative data for more in-depth and longer-term follow-up, use samples and data in future research, and ask for permission to contact participants for future research opportunities.

The consent form will be signed and dated by both the participant and the Site Investigator/Delegate, and a copy will be given to the participant, and one copy will be retained at the study site.

3.5.4. Study Contacts/Follow-up Schedule

Study contacts will be made at baseline, post-vaccination, delivery and across the postpartum period. The extent of data and sample collection will vary by time-point (**See Figure 2**).

- Visit 1 (V1) will occur prior to 1st dose (if applicable)
- Visit 2 (V2) will occur ≥ 14 days after 1st dose and prior to 2nd dose
- Visit 3 (V3) will occur ≥ 14 days after 2nd dose and prior to Visit 4
- Visit 4 (V4) will occur 90 days \pm 14 days after last dose
- Visit 5 (V5) will occur 180 days \pm 14 days after last dose
- **Baseline** questionnaire will occur at the time of enrollment prior to or during V2, following participant consent.
- **General follow-up** questionnaires may be completed during the study visit or completed prior to the following study visit
- **Reactogenicity questionnaire 1 (RQ1)** must be completed prior to 2nd dose
- **Reactogenicity questionnaire 2 (RQ2)** must be completed within 30 days after last dose (for single vaccine or second dose)
- **Delivery follow-up** will include secondary data collection (to reduce burden on participants during the hospital delivery admission), and sample collection.

[figure not shown]
[figure not shown]

Figure 2. Study contacts/follow-up schedule.

3.5.5. Communication with participants for follow-ups visits and/or reminders for questionnaires

We will collect the preferred contact information (i.e., telephone number and/or email address) of participants at the time of consent to facilitate follow-up visits and/or reminders. Participants agreeing to email communication will be informed that communication via email is not absolutely secure. The study team will contact the participant for the purposes of booking and reminding participants of follow-up appointments and completion of study questionnaires. No sensitive personal information will be shared via any text-based communication (e.g., email, SMS text, post).

3.5.6. Participant Compensation

Participants will be compensated for parking or bus fare for all in-person visits scheduled outside of their regularly scheduled obstetrical clinic visit to the study site, to offset the costs of participation. In addition, participants will be provided with a \$5 gift card to a coffee shop at each in-person study visit to acknowledge their time participating in the study. A \$5 gift card to a coffee shop will also be given to participants who complete all study questionnaires.

3.5.7. Premature Withdrawal/Discontinuation

[figure not shown]
Reasons for participant withdrawal from the study will be documented. If a participant no longer wants their samples to be used in this research, they can request to have their samples destroyed. However, samples will not be destroyed if they have been used in their entirety, or if they have been shared with a 3rd party. Collected data and test results from samples already collected for the study will be retained such that withdrawal will only affect future data or sample collection. Participants who withdraw from the study will no longer be contacted.

If a participant does not complete a study questionnaire, or does not contribute one or more study samples (by choice, or due to other factors) they are free to do so. Incomplete data or bio-sample collection will not exclude participants from the study.

An individual's participation may also be terminated prematurely at the request of the Site Investigator/Delegate, or the Study Coordinating Centre.

3.6. Data Collection

This study will involve a combination of primary and secondary data collection.

Sex and Gender-based Analysis Plus (SGBA+) considerations

All pregnant participants will be biological females, however through our primary data collection tools we will be able to gather information on gender and gender-related factors that shape the pregnancy and postpartum experience including self-reported ethnicity, age, income, education, and geography. In addition to maternal sex, we will collect information on current gender identity, sexual orientation and partnership status. All documents will be written with gender-inclusive language to improve engagement with members from the LGBTQ+ community. Infant biological sex assigned at birth will be used to detect effects within sex strata and potential biological differences influenced by infant hormones levels circulating in the blood at time of sampling.

3.6.1. Primary Data Collection

Primary data collection forms will be made available electronically (as fillable PDF documents or online forms), but may also be provided/completed in hard copy to suit the unique needs of each participating research site and participant visit. Where necessary, participants will have the option to have data collection forms mailed to them with pre-paid return envelopes to the research site or SCC. Thus, questionnaires can be completed at-home by participants, in-person during a scheduled study visit, or over the telephone with the Investigator/Delegate, as needed.

The primary data collection schedule is summarized in Table 1.

Table 1. Primary Data collection schedule for vaccinated participants

	Enrollment	Post-vaccination Follow-up ¹				
		RQ1 and RQ2	V2	V3	V4	V5
Baseline Questionnaire	X					
Reactogenicity Questionnaire		X				
General Follow-up Questionnaire			X	X	X	X

¹Post-vaccination follow-up may occur or extend into the postpartum period depending on when participants enroll into the study.

[figure not shown]
- If participant is getting a 2-dose vaccine, and dose 2 scheduling is delayed (for any reason – federal/provincial/local recommendations, participant reasons), data and sample collection will be done every 3 months until dose 2 is administered.
- Baseline questionnaire must be completed prior to or at V2.
- General questionnaires must be completed prior to or at following study visit.
- RQ1 must be completed prior to 2nd dose.
- RQ2 must be completed within 30 days after last dose (for single vaccine or second dose)*
- If participant is getting a 2-dose vaccine, and dose 2 scheduling is delayed (for any reason – federal/provincial/local recommendations, participant reasons), data and sample collection will be done every 3 months until dose 2 is administered.

Baseline questionnaire

A baseline questionnaire will be administered **at enrollment** to document participant characteristics. We will collect socio-demographic information (e.g., maternal age, ethnicity, occupation, education, household income), medical and obstetrical histories (e.g., parity, pre-existing conditions), receipt of blood products or other vaccines in pregnancy, other lifestyle risks (e.g., tobacco, alcohol and other substance use), and previous SARS-CoV-2 infection history. Key factors influencing participant decision-making to receive the COVID-19 vaccine (decision needs, information access, family and societal pressures) will be documented.

Reactogenicity questionnaires

After each COVID-19 vaccine dose we will collect priority variables for studying COVID-19 vaccination in the maternal-newborn population¹¹:

- **COVID-19 vaccine data:** vaccine product (e.g., Moderna, Pfizer-BioNTech, Janssen (Johnson & Johnson), Oxford-AstraZeneca, etc.), dose number (one or two) and date received (to calculate timing of exposure in pregnancy or postpartum relative to delivery, and length of time between doses, if applicable). Scheduled dates of second COVID-19 vaccine doses (if applicable) will also be collected.
- **Reactogenicity:** injection site (e.g., bruising, swelling, pain) and systemic (e.g., fever, headache, muscle ache, fatigue) reactogenicity since the participant received the most recent vaccine dose.

General follow-up questionnaires

At each subsequent follow-up timepoint:

- **If the participant is still pregnant:** We will ask about significant changes in maternal and fetal health (e.g., new medical diagnoses or illnesses), maternal receipt of any blood products or other vaccinations, and any new maternal COVID-19 diagnoses (including variant information if known) since the last study visit.
- **If the participant is postpartum:** We will ask about significant changes in maternal and infant health (e.g., new medical diagnoses or illnesses), receipt of any blood products or other vaccinations (mother or infant), infant feeding method (e.g., mother's own breastmilk/chestmilk, donor milk, formula, other, combination) and infant growth (e.g., weight, length). We will also ask about any new maternal or infant COVID-19 diagnoses (including variant information if known) since the last study visit.

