3.7. Sample Collection, Shipping and Analysis

3.7.1. Sample collection

Participants will be asked to contribute biological samples. We will allow participants to choose the scope of sample collection at each time-point. Samples will include maternal blood; breastmilk/chestmilk (postpartum collection only); and newborn blood (including cord blood at delivery). (Table 2)

Sampling will be coordinated alongside routine clinical collections where possible to minimize burden to participants. If participating hospital sites have sufficient capacity and resources, participants will be given the option to (1) return to the hospital or affiliated community clinic for sample collection/drop-off; (2) schedule a home visit with a research nurse/coordinator for sample collection/pick-up; (3) mail-in samples, if dried blood spot is preferred by the participant.

For the protection of all parties, both the Site Investigator/Delegate conducting the appointment and the participant will be directed to answer a series of self-assessment questions to assess likelihood or risk of COVID-19 infection before attending in-person visits.

[figure not shown]

Table 2. Sample collection schedule for vaccinated participants

	Visit 1	Post-vaccination Follow-up ³				Delivery
		Visit 2	Visit 3	Visit 4	Visit 5	
Maternal blood ¹	X	X	X	X	X	X
Baby(ies) blood ^{1,2}		X	X	X	X	
Breast/Chest milk ²		X	X	X	X	X
Cord blood						X
Placenta						X

¹Blood samples will be taken as peripheral blood draws, or as dried blood spot samples, as per participant preferences.

²Baby(ies) and milk samples will only be collected after delivery.

³Post-vaccination follow-up schedule will be the same for all vaccine doses (dose 1 or dose 2, if applicable).

- Visit 2 will be scheduled for ≥ 14 days after 1st dose and prior to 2nd dose
- Visit 3 will be scheduled for ≥ 14 days after 2nd dose and prior to visit 4
- Visit 4 will be scheduled for 90 days \pm 14 days after last dose
- Visit 5 will be scheduled for 180 days \pm 14 days after last dose
- If participant is getting a 2-dose vaccine, 1-month follow-up for data collection for dose 1 will occur before dose 2 administration.
- If participant is getting a 2-dose vaccine, and dose 2 scheduling is delayed (for any reason – federal/provincial/local recommendations, participant reasons), data and sample collection will be done approximately every 3 months (~120 days) until dose 2 is administered

Blood samples

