- **Stop the Spread Ottawa (SSO) participants:** Non-pregnant females of reproductive age without known history of SARS-CoV-2 infection who received at least one COVID-19 vaccine dose. SSO is an ongoing Ottawa-based, 1000-person prospective cohort study designed to investigate the SARS-CoV-2-specific immune response on COVID-19 convalescent and COVID-19 vaccinated individuals. A total of 126 non-pregnant individuals of reproductive age who have received a COVID-19 vaccine have been enrolled to date. Participants provide monthly blood samples post-vaccination using the same protocols described for the PLAN-V study protocol and are followed for 10 months, allowing for comparison across the PLAN-V time points.

Exposures: The exposure of interest is maternal COVID-19 vaccination in pregnancy (PLAN-V Study) or while not pregnant (SSO Study)

Outcome Measures: The primary immunological outcome measure will be antibody titres acquired from COVID-19 vaccination in pregnant women/individuals will be compared to those of non-pregnant women/individuals. Secondary outcomes will include vaccine reactogenicity, as well as nature and frequency of vaccine-related adverse events.

Sample analysis. Blood serum samples will be evaluated for SARS CoV-2 specific antibodies and neutralizing antibody titres, as well as antibody subclass distributions where appropriate. Samples will be analyzed using the methods described in Section 3.7.3.

Data Sources: Immunogenicity data (including seroconversion rates and antibody titres), vaccine-related data (including product information, reactogenicity and adverse events), and participant characteristics (including sociodemographics, health behaviour risks and medical history) will come from the PLAN-V and the SSO study datasets. The PLAN-V and SSO datasets are both stored at the OHRI, and data elements are aligned thereby facilitating robust comparison of outcome measures.

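### Reactogenicity has no fixed recall period, and RQ1 is limited only by dose 2 while RQ2 is due within 30 days, so dose 1, dose 2 and SSO frequencies may not be comparable

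*Protocol*

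**What the plan says.** All references are to the protocol.

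- **Question asked (Section 3.6.1, Reactogenicity questionnaires).** After each dose the form records injection-site reactions and "systemic (e.g., fever, headache, muscle ache, fatigue) reactogenicity since the participant received the most recent vaccine dose". No length of period is given, and date of symptom onset is not among the items listed.
- **Deadline for dose 1 (Sections 3.5.4 and 3.6.1).** "RQ1 must be completed prior to 2nd dose". There is no limit in days and no earliest day.
- **Deadline for the last dose (same sections).** "RQ2 must be completed within 30 days after last dose". This covers a single-dose vaccine or a second dose. Again there is no earliest day.
- **Delay of dose 2 (Section 3.7.1; similarly 3.6.1).** If dose 2 is late, "data and sample collection will be done approximately every 3 months (~120 days) until dose 2 is administered".
- **Enrolment (Section 3.2.1).** Women who have already had one dose in the current pregnancy may enrol, so RQ1 can be retrospective.
- **Another dose 1 time point (Section 3.7.1, notes to Table 2).** For two-dose vaccines, "1-month follow-up for data collection for dose 1 will occur before dose 2 administration". Sections 3.5.4 and 3.6.1 do not mention this follow-up, and it is not linked to RQ1.
- **Use of the data (Objective 4: SSO Sub-study, Outcome Measures).** "Secondary outcomes will include vaccine reactogenicity, as well as nature and frequency of vaccine-related adverse events". Section 3.1 also names reactogenicity among the things to be explored.

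**The concern.** Because the question runs from the dose to the day the form is filled in, the completion deadline also caps the symptom period. For the last dose the cap is 30 days. For dose 1 it is the whole gap between doses, which the protocol expects may run to months. Within those caps the actual period can be anything from the day of vaccination upwards.

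Headache, muscle ache and fatigue also occur without vaccination, and more of them accrue over a longer period. The protocol lists no symptom record from before vaccination, and the baseline form may be completed as late as Visit 2, at least 14 days after dose 1. A reported frequency therefore mixes true reactions with an amount of background that depends on when each woman happened to complete her form.

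At stake are the dose 1 and dose 2 frequencies, comparisons between women with short and long dose gaps, and the pregnant versus non-pregnant comparison in Objective 4. A later analysis could not repair this if onset dates are not captured. The recorded dose dates give the gap between doses, but they do not separate a fever on day 2 from a headache on day 80.

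**Working it through.** The protocol gives no reactogenicity rate, background rate or power for this outcome, so there is no figure of its own to reproduce. The check has two parts.

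**1. The rules side by side**

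| | Dose 1 (RQ1) | Last dose (RQ2) |
|---|---|---|
| Symptom period starts | at the dose | at the dose |
| Symptom period ends | when the form is completed | when the form is completed |
| Earliest completion | none stated | none stated |
| Latest completion | dose 2 | 30 days |
| Completion after late enrolment | possible | not beyond 30 days |

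The two forms have equal periods only if completion times happen to coincide. Section 4 says analyses will account for vaccination timing, product and number of doses, among other factors. It does not name recall length or dose interval.

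**2. Illustration of size**

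Inputs:
- *d*, days from dose to form. The 30 days is the RQ2 deadline and the 120 days is the protocol's own gloss on its three-month interval. That every form is completed on those days is an assumption.
- *r*, daily chance of a first unrelated headache, ache or fatigue: 0.5%, 1% or 2%. Assumed; no document gives it.
- *R*, true reactogenicity, equal after both doses: 30% or 50%. Assumed.
- Perfect recall, with every background symptom reported as a reaction. Assumed.

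Formulas:
- Background alone: B(d) = 1 − (1 − r)^d
- Reported frequency: P(d) = 1 − (1 − R)(1 − r)^d
- Artificial dose 1 excess: P(120) − P(30) = (1 − R) × [B(120) − B(30)]

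| r per day | B(7) | B(30) | B(120) | B(120) − B(30) | Excess, R = 30% (× 0.7) | Excess, R = 50% (× 0.5) |
|---|---|---|---|---|---|---|
| 0.5% | 3.4% | 14.0% | 45.2% | 31.2 points | 21.9 points | 15.6 points |
| 1% | 6.8% | 26.0% | 70.1% | 44.0 points | 30.8 points | 22.0 points |
| 2% | 13.2% | 45.5% | 91.1% | 45.7 points | 32.0 points | 22.8 points |

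As an example, with r = 1% and R = 30%, the reported frequency is 1 − 0.7 × 0.99^30 = 48.2% at 30 days and 1 − 0.7 × 0.99^120 = 79.0% at 120 days, although the true rate is 30% in both.

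Sensitivity to completion time, at R = 30%:
- RQ1 at 90 days instead of 120: the excess falls to 15.6, 23.4 and 26.8 points for the three values of r.
- RQ1 at 21 days against RQ2 at 30: the sign reverses, and dose 1 looks better by 2.8, 4.9 and 7.6 points.
- Both forms restricted to onset in the same period: the difference is zero. With a 7-day period the remaining background is 0.7 × B(7), or 2.4, 4.8 and 9.2 points, the same for both doses.

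**The case against.** The strongest reply is that a completion deadline is not a symptom window. The questionnaire itself is not in the document and may ask about onset or set its own period. Section 3.6.1 says the data are collected after each dose, and nothing says RQ1 is held until just before dose 2. Section 3.7.1 plans a 1-month dose 1 follow-up, and a footnote to Table 2 says the follow-up schedule is the same for each dose. If these govern RQ1, both doses have about one month. Reactogenicity is also absent from the main outcome lists (Sections 3.4.1 and 3.4.2), and no formal dose 1 versus dose 2 comparison is planned.

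Much of this limits the point without removing it. Where the question runs from the dose to completion, the deadline does bound the period, and the protocol states no other bound. A form completed at one month and before dose 2 would satisfy both rules, so the 1-month line does not contradict the RQ1 rule, but the protocol does not tie the two together. Capturing onset is a matter of data collection, so it cannot be left to an analysis plan.

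Three stronger readings are tempting but not supported:
- *Dose 1 will look worse the longer dose 2 is delayed.* This needs RQ1 to be completed late and background symptoms to be remembered. Early completion, forgetting or a dose gap under 30 days pushes the other way.
- *The excess would be 31 to 46 points.* That is the difference in background alone, and it applies only if true reactogenicity is zero.
- *SSO frequencies are on a different scale.* No SSO symptom period is documented, and Objective 4 says the data elements are aligned. What can be said is that no common period is stated.

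**Conclusion.** The point holds in a limited form. As written, the rules allow the symptom period to differ between doses and between women, with no control over the direction of the resulting bias. Dose 1, dose 2 and SSO frequencies may therefore not be comparable.

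The illustrated excess, about 22 to 32 points at a true rate of 30% and 16 to 23 at 50%, rests on assumed background rates, complete recall, and every RQ1 at 120 days against every RQ2 at 30. It shows what the rules permit and is not a forecast; if RQ1 is completed soon after dose 1, there is no such excess.

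This does not touch the primary immunogenicity outcomes. It is worth correcting because reactogenicity is a named secondary outcome of Objective 4 and the study aims to inform counselling.

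**What to change.** 1. In Sections 3.5.4 and 3.6.1, have RQ1 and RQ2 ask about the same fixed period after each dose (for example the first 7 days), record the date of symptom onset, and require completion after that period has ended.
2. Base reactogenicity frequencies on onset within that period. Apply the same period to the SSO data in Objective 4 where those data allow, and say so where they do not.
3. Report forms completed late, including those from women enrolled long after dose 1, separately or in a sensitivity analysis.
4. State whether the 1-month dose 1 follow-up in Section 3.7.1 governs RQ1, and reconcile Sections 3.5.4, 3.6.1 and 3.7.1.

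The cost is a wording change to one questionnaire and the matching protocol sections. The downside is that dose 1 reports from late enrollees either rest on longer recall or contribute only to the sensitivity analysis; the documents do not show how many of the planned 150 women this would be. A common period removes the difference caused by unequal periods. It does not remove background symptoms altogether, but a short period keeps them small and equal across doses.
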